## 1.3 Clinical Development of Obicetrapib

Both single ascending dose (TA-8995-01) and multiple ascending dose (TA-8995-02) studies have been conducted in healthy volunteers. A formal thorough QT/QTc study (TA-8995-04) has been completed and obicetrapib was shown to have no effect on corrected QT interval by Fridericia. A drug-drug interaction study (TA-8995-05) has also been conducted; this study showed no significant effect of obicetrapib on P-glycoprotein activity, but this study showed that obicetrapib is a mild inducer of cytochrome P450 3A4. A mass balance study in healthy males concluded that obicetrapib is steadily absorbed, and the principal route of excretion was in the feces (TA-8995-07). Finally, bioequivalence between obicetrapib capsule and tablet formulations was investigated (TA-8995-08) and established.

The first patient study conducted was a Phase 2 clinical study (TA-8995-03) in Denmark and the Netherlands where the aim was to evaluate the optimal dose of obicetrapib alone and in combination with statins in participants with mild dyslipidemia. This study concluded that a daily dose of 5 mg obicetrapib resulted in an LDL-C reduction of 45.3%, an ApoB reduction of 33.6%, an HDL-C increase of 157.1%, an ApoA1 increase of 57.5%, and a significant increase in HDL-C efflux capacity. A second patient study (TA-8995-06) was conducted where the effect of obicetrapib on Lp(a) was investigated following 12 weeks of treatment. There was a statistically significant reduction in Lp(a) levels following 12 weeks of treatment; however, the magnitude of the changes (approximately a 10% reduction) was not likely to be clinically relevant.

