# 1.4 Rationale for Obicetrapib and Ezetimibe Combination Therapy

An important therapeutic goal is to maximize LDL-C reduction for patients who cannot tolerate statin therapy. Ezetimibe selectively inhibits intestinal cholesterol absorption. Ezetimibe used as monotherapy for patients with hypercholesterolemia significantly reduces serum LDL-C levels, as evidenced by a meta-analysis of 8 randomized, double-blind, placebo-controlled studies, with a statistically significant mean reduction in LDL-C of 18.58% compared with placebo. Ezetimibe in combination with statin therapy further reduces LDL-C levels. A meta-analysis of 27 studies, including more than 21,000 patients, demonstrated a 15.1% greater reduction in LDL-C in patients treated with statin and ezetimibe in combination compared with statin alone.  Although there is a lack of evidence that ezetimibe monotherapy reduces cardiovascular events, the IMPROVE-IT study, 16 in which simvastatin 40 mg daily was compared with a combination of simvastatin 40 mg plus ezetimibe 10 mg in 18,144 patients with acute coronary syndrome, demonstrated a modest but statistically significant further reduction in future cardiovascular events (a 2% absolute risk reduction over 7 years) in the combination group compared with statins alone. These large long-term studies have also demonstrated an excellent safety profile for ezetimibe. Importantly, additional Mendelian randomization studies have revealed that the CETP inhibitor HMGCR inhibitor interaction does not occur when a CETP inhibitor is combined with ezetimibe.

Accordingly, to evaluate the potential for ezetimibe to further augment LDL-C as well as ApoB reduction achieved by a CETP inhibitor, this study will test the effect of obicetrapib and ezetimibe combination therapy compared to obicetrapib monotherapy and ezetimibe monotherapy in participants with mild dyslipidemia.

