# 3.1.1 Screening Period

At the Screening Visit (Visit 1), participants will be required to sign an informed consent form (ICF) before any study-related procedures are performed. After signing the ICF, participants will be assessed for study eligibility. Participants will also receive counselling regarding the Therapeutic Lifestyle Changes (TLC) diet and will receive instructions on how to follow this diet (see Appendix C). Participants will be required to begin the diet starting at the Screening Visit.

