#### 4 SELECTION AND WITHDRAWAL OF PARTICIPANTS

#### 4.1 Inclusion Criteria

Participants who meet all of the following criteria will be eligible to participate in the study:

- 1. Understanding of the study procedures, willingness to adhere to the study schedules and diet, and agreement to participate in the study by giving written informed consent prior to Screening procedures;
- 2. Men or women 18 to 70 years of age, inclusive;
  - o Women may be enrolled if all 3 of the following criteria are met:
    - They are not pregnant;
    - They are not breastfeeding; and
    - They do not plan on becoming pregnant during the study;
  - O Women of childbearing potential must have a negative urine pregnancy test at the Screening Visit. Note: Women are not considered to be of childbearing potential if they meet 1 of the following criteria as documented by the Investigator:
    - They have had a hysterectomy or tubal ligation at a minimum of 1 cycle prior to signing the ICF; or
    - They are post-menopausal, defined as ≥1 year since their last menstrual period for women ≥55 years of age or ≥1 year since their last menstrual period and have a follicle-stimulating hormone (FSH) level in the menopausal range for women <55 years of age;

  - O Women of childbearing potential must agree to use an effective method of avoiding pregnancy from the Screening Visit to 90 days after the last visit. Men whose partners are of childbearing potential must agree to use an effective method of avoiding pregnancy from the Screening Visit to 90 days after the last visit. Effective methods of avoiding pregnancy are contraceptive methods with a Pearl index of <1 used consistently and correctly (including implantable contraceptives, injectable contraceptives, oral contraceptives, transdermal contraceptives, intrauterine devices, diaphragm with spermicide, male or female condoms with spermicide, or cervical cap) or a sterile sexual partner;
- 3. Fasting LDL-C levels >2.5 mmol/L (>100 mg/dL) and <4.5 mmol/L (<175 mg/dL) and TG levels <4.5 mmol/L (<400 mg/dL) (Visit 1); and
- 4. Willingness to maintain a stable diet and physical activity level throughout the study.

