2.2.4 Sample Size Determination

A sample size of at least 100 evaluable participants (ie, 25 participants per treatment group) will provide >90% power to detect a 30% difference in LDL-C reduction at Day 57 (SD 15%) for the combination therapy group compared to the placebo group at a 2-sided significance level of 0.05.

The sample size for this study was determined in order to provide sufficient power (>80%) for the analyses of the primary efficacy endpoint and secondary efficacy endpoints described in Section 2.3. The sample size calculations used values reported from a previous clinical trial involving obicetrapib (TA-8995) as a starting point for the assumptions of the treatment difference and standard deviation¹. This sample size will also contribute sufficient participant exposure and safety data.

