2.3.3 Exploratory Efficacy Endpoints

The exploratory efficacy endpoints include the following:

- Percent change from Day 1 to Day 57 in ApoB for the ezetimibe monotherapy group compared to the placebo group;
- Pairwise comparisons among the various treatment groups for the percent change from Day 1 to Day 57 in non-HDL-C, VLDL-C, HDL-C, TG, ApoE, and HDL-ApoE (with and without ApoC3);
- Pairwise comparisons among the various treatment groups for the proportion of participants at Day 57 that achieve LDL-C <2.6 mmol/L (<100 mg/dL), LDL-C <1.8 mmol/L (<70 mg/dL), and LDL-C <1.3 mmol/L (<50 mg/dL);

NewAmsterdam Pharma BV	CONFIDENTIAL	Statistical Analysis Plan
Protocol TA-8995-303		Version V2.0, 24 June 2021

- Pairwise comparisons among the various treatment groups for the change from Day 1 to Day 57, Day 1 to Week 12, and Day 1 to Week 16 in the mean trough plasma levels of obicetrapib; and
- Pairwise comparisons among the various treatment groups for the change from Day 1 to Day 57, Day 1 to Week 12, and Day 1 to Week 16 in CETP mass.

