3.4.3 Exploratory Efficacy Endpoints

Similar MMRM models will be used for the following analysis:

- Percent change from Day 1 to Day 57 in ApoB for the ezetimibe monotherapy group compared to the placebo group;
- Pairwise comparisons among the various treatment groups for the percent change from Day 1 to Day 57 in non-HDL-C, VLDL-C, HDL-C, TG, ApoE, and HDL-ApoE (with and without ApoC3);
- Pairwise comparisons among the various treatment groups for the change from Day 1 to Day 57, Day 1 to Week 12, and Day 1 to Week 16 in the mean trough plasma levels of obicetrapib; and
- Pairwise comparisons among the various treatment groups for the change from Day 1 to Day 57, Day 1 to Week 12, and Day 1 to Week 16 in CETP mass.

The proportion of subjects at Day 57 that achieve LDL-C <2.6 mmol/L (<100 mg/dL), LDL-C <1.8 mmol/L (<70 mg/dL), and LDL-C <1.3 mmol/L (<50 mg/dL) will be examined through Logistic Regression Models for binary variables with covariates of the treatment groups and the Baseline variable.

The Logistic Regression Model will be implemented using SAS[®] Proc LOGISTIC. The sample SAS code can be found below:

NewAmsterdam Pharma BV	CONFIDENTIAL	Statistical Analysis Plan		
Protocol TA-8995-303		Version V2.0, 24 June 2021		

Note: USUBJID = unique subject identifier TREATMENT = 0 (Placebo), 1 (Ezetimibe monotherapy), 2 (Obicetrapib monotherapy), 3 (Combination therapy) BASE = Baseline value LDLC100 = LDL_C value less than 100mg/dL at DAY57 (YES/NO) for example proc logistic data= LDL_C; Class TREATMENT(ref=0) / Param= Ref; Model LDLC100 = TREATMENT BASE / alpha=0.05 expb plcl plrl orpvalue lackfit; Ods output ParameterEstimates= Log_LDLC100_ParameterEstimates CLoddsPL= Log_ LDLC100_OddsRatios ; Run;

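### The logistic models for LDL-C targets have no rule for a treatment arm with 0% or 100% responders, which is the expected outcome for placebo at <70 and <50 mg/dL

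*SAP*

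**What the plan says.** SAP 2.3.3 lists the endpoint as "Pairwise comparisons among the various treatment groups for the proportion of participants at Day 57 that achieve LDL-C <2.6 mmol/L (<100 mg/dL"), with <70 and <50 mg/dL as the other two targets. Four arms give six pairs per target, so 18 comparisons in all.

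SAP 3.4.3 states that these proportions "will be examined through Logistic Regression Models for binary variables with covariates of the treatment groups and the Baseline variable". The sample code is "Model LDLC100 = TREATMENT BASE / alpha=0.05 expb plcl plrl orpvalue lackfit; Ods output ParameterEstimates= Log_LDLC100_ParameterEstimates". Placebo is the reference level. The code saves two tables: `ParameterEstimates`, which carries the Wald tests, and `CLoddsPL`, the profile-likelihood odds-ratio limits. It has no `FIRTH` option and no `EXACT` statement. Protocol 9.2.1.2 gives the same model and promises nominal p-values where applicable. Neither document has a rule for an arm at 0% or 100%.

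**The concern.** Eligibility requires a screening LDL-C above 100 mg/dL (Protocol 4.1). A placebo participant near that limit must fall by about 30% to get below 70 and by about 50% to get below 50. Few will, and with 25 per arm the likely placebo count is zero.

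When an arm has no responders, or only responders, its treatment coefficient has no finite maximum-likelihood value. The odds ratio against it is then infinite (or zero), one profile-likelihood limit is infinite, and the Wald standard error grows so large that p approaches 1. If both arms of a pair have no responders, the pair has no estimate and neither limit exists.

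The code takes as reference the arm most likely to be empty, so all three printed treatment coefficients fail together. A reader of the Wald table could see p near 1 for 17/25 versus 0/25, where Fisher's exact p is 2 × 10⁻⁷. A fallback chosen after the empty arm has been seen would be post hoc.

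**Working it through.** **The plan's own figure.** SAP 2.2.4 states more than 90% power for a 30-point difference, SD 15, 25 per arm. The noncentrality is 30 / (15 × √(2/25)) = 7.07, so power exceeds 99.99% and the statement holds. The documents give no figure for the binary endpoints.

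**Inputs from the documents.** 25 per arm and SD 15 (SAP 2.2.4); "a daily dose of 5 mg obicetrapib resulted in an LDL-C reduction of 45.3" percent (Protocol 1.3); for ezetimibe a "mean reduction in LDL-C of 18.58% compared with placebo" (Protocol 1.4).

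**Assumptions.** Mean placebo change 0. Day 1 LDL-C uniform on 100-175 mg/dL. Combination fall 55.5%, from multiplying the two single-drug effects: 1 − (1 − 0.453)(1 − 0.1858) = 0.555. Percent change normally distributed.

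**Chance of an empty arm.** For target t, mean change m and SD s, the response probability p is the average over baseline b of Φ{[100(t/b − 1) − m]/s}. Then P(no responder) = (1 − p)^25 and P(all respond) = p^25. For a placebo participant with baseline 100 and target 70, Φ(−30/15) = 0.023. At baseline 137.5 the required fall is 49.1%, and Φ(−3.27) = 0.0005. Averaged over 100-175, p = 0.0029 and (1 − 0.0029)^25 = 0.93.

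| Arm | Target (mg/dL) | p | Mean responders of 25 | P(0/25) | P(25/25) |
|---|---|---|---|---|---|
| Placebo | <100 | 0.099 | 2.5 | 7% | 0% |
| Placebo | <70 | 0.0029 | 0.07 | 93% | 0% |
| Placebo | <50 | 0.00005 | 0.00 | 99.9% | 0% |
| Ezetimibe | <70 | 0.047 | 1.2 | 30% | 0% |
| Ezetimibe | <50 | 0.0033 | 0.08 | 92% | 0% |
| Obicetrapib | <50 | 0.142 | 3.5 | 2% | 0% |
| Combination | <100 | 0.945 | 23.6 | 0% | 24% |
| Combination | <70 | 0.669 | 16.7 | 0% | 0% |
| Combination | <50 | 0.328 | 8.2 | 0% | 0% |

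**Sensitivity.** The limits in Protocol 4.1 apply at screening, and Protocol 3.1.1 adds "Participants will be required to begin the diet starting at the Screening Visit", so Day 1 values can fall below 100. The check was therefore repeated over 24 scenarios: SD 10, 15 or 20; placebo fall 0 or 5%, with ezetimibe shifted equally; and four baseline shapes, one reaching down to 90 mg/dL.

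| P(no responder) | All 24 scenarios | SD held at 15 |
|---|---|---|
| Placebo, <70 | 35-99.9% | 68-94% |
| Placebo, <50 | at least 89% | at least 98.8% |
| Ezetimibe, <50 | 30-99.9% | 71-92% |

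**How many odds ratios fail.** If π is an arm's chance of being at 0/25 or 25/25, a pair fails with probability 1 − (1 − π₁)(1 − π₂). Summed over six pairs, this gives 1.0 at <100, 3.4 at <70 and 4.9 at <50. The total is about 9.2 of 18 (9.3 by simulation; 5.6 with SD 20 and a 5% placebo fall). Against placebo alone it is about 6.3 of 9. Obicetrapib versus combination is rarely affected at <70 (0%) or <50 (2%), and fails in about a quarter of trials at <100.

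**What the fitted model prints.** The four-arm model with baseline was fitted to simulated base-case trials with no placebo responder, 250 per scenario. Results for combination versus placebo:

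| Target | Mean counts of 25 | Wald p<0.05 | ML likelihood-ratio p<0.05 | ML profile limits for the odds ratio |
|---|---|---|---|---|
| <70 | 16.7 vs 0 | 0% | 100% | lower about 41, upper infinite |
| <50 | 8.4 vs 0 | 0% (median p 1.0) | 100% | lower 6.3 (median), upper infinite |

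**With Firth penalisation.** At <50, the penalised likelihood-ratio test rejects in 99% of the same trials. The typical odds ratio is 27, with 95% limits of about 3.0 to 3,700.

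**Risk difference.** For 8/25 versus 0/25 it is 32 points. The Wilson limits are 17.2% to 51.6% and 0% to 13.3%. The Newcombe limits are 32 − √(14.8² + 13.3²) = 12 and 32 + √(19.6² + 0²) = 52.

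**The case against.** The strongest reply is that the plan already requests output that survives an empty arm. The `plcl` and `plrl` options give profile-likelihood limits, and a lower limit of 41 beside 17/25 versus 0/25 would hardly be read as no effect. This stands in part: the direction and a minimum size are recoverable for obicetrapib or combination versus placebo. There is still no point estimate and no upper limit, and nothing at all when placebo and ezetimibe are both empty. The plan also does not say which p-value is reported, or which test lies behind `orpvalue`.

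The endpoints are exploratory and unadjusted, and counts and percentages are reported anyway. That limits the consequence and is conceded.

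The combination fall of 55.5% is not in the documents. With the 30-point sample-size difference instead, the combination arm averages 3.8/25 at <70 and 0.55/25 at <50. The contrast is then less striking, but the empty placebo arm does not depend on this input. At <70 the probability does depend on the SD: it drops to 35% with SD 20, a 5% placebo fall and baselines of 100-140. Only placebo at <50 is near certain throughout.

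The code is labelled as a sample, and SAP section 6 refers to a separate programming specification. A fallback might sit there, but a document outside the plan cannot be counted as supplying one.

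**Conclusion.** The concern holds. Run as written, the model will very probably give non-finite odds ratios, and Wald p-values near 1, for all comparisons with placebo at <50 mg/dL (at least 89% in every scenario). At the plan's own SD it will probably do so at <70 as well (68-94%). About half of the 18 pairwise odds ratios have no finite estimate in the base case. These figures rest on the assumed placebo change, baseline distribution and normality of percent change, varied as shown.

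The damage is confined to exploratory endpoints with nominal p-values. Comparisons between arms with intermediate rates, and the primary and secondary analyses, are unaffected. It should be corrected because the failure is foreseeable and the remedy is cheap before unblinding.

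**What to change.** In SAP 3.4.3:

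- Add the `FIRTH` option with penalised profile-likelihood 95% limits for the target-attainment models. State whether it applies to all of them or only when an arm is at 0% or 100%; the latter is the minimum.
- State that Wald p-values are not reported for contrasts involving such an arm.
- Report the risk difference with a score or exact 95% interval for every pairwise comparison.

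The cost is one model option, one sentence and one table column. There are statistical costs too. Firth shrinks odds ratios where both arms are intermediate: obicetrapib versus combination at <50 has a median of 3.3, against 3.9 by maximum likelihood. Intervals against an empty arm stay very wide. The Firth test is also more conservative: for obicetrapib versus placebo at <50 it rejected in 40% to 47% of simulated trials, against about 70% for the ordinary likelihood-ratio test.

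A smaller alternative is to report profile-likelihood limits and likelihood-ratio p-values whenever an arm is empty or full. That keeps the power but gives no finite odds ratio, so the risk difference would be needed even more.

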## 7 EFFICACY ASSESSMENTS

The primary efficacy endpoint is percent change from Day 1 to Day 57 in LDL-C for the combination therapy group compared to the placebo group.

The secondary efficacy endpoints include the following, in hierarchical order:

- Percent change from Day 1 to Day 57 in LDL-C for the obicetrapib monotherapy group compared to the placebo group;
- Percent change from Day 1 to Day 57 in ApoB for the combination therapy group compared to the placebo group;
- Percent change from Day 1 to Day 57 in ApoB for the obicetrapib monotherapy group compared to the placebo group;
- Percent change from Day 1 to Day 57 in LDL-C for the combination therapy group compared to the ezetimibe monotherapy group;
- Percent change from Day 1 to Day 57 in LDL-C for the obicetrapib monotherapy group compared to the ezetimibe monotherapy group;
- Percent change from Day 1 to Day 57 in LDL-C for the ezetimibe monotherapy group compared to the placebo group; and
- Percent change from Day 1 to Day 57 in ApoB for the combination therapy group compared to the ezetimibe monotherapy group.

The exploratory efficacy endpoints include the following:

- Percent change from Day 1 to Day 57 in ApoB for the ezetimibe monotherapy group compared to the placebo group;
- Pairwise comparisons among the various treatment groups for the percent change from Day 1 to Day 57 in non-HDL-C, VLDL-C, HDL-C, TG, ApoE, and HDL-ApoE (with and without ApoC3);
- Pairwise comparisons among the various treatment groups for the proportion of participants at Day 57 that achieve LDL-C <2.6 mmol/L (<100 mg/dL), LDL-C <1.8 mmol/L (<70 mg/dL), and LDL-C <1.3 mmol/L (<50 mg/dL);

- Pairwise comparisons among the various treatment groups for the change from Day 1 to Day 57, Day 1 to Week 12, and Day 1 to Week 16 in the mean trough plasma levels of obicetrapib; and
- Pairwise comparisons among the various treatment groups for the change from Day 1 to Day 57, Day 1 to Week 12, and Day 1 to Week 16 in CETP mass.

Blood samples for lipid profile must be obtained under fasting conditions (ie, after the participant has fasted for  $\geq 10$  hours). For the purposes of this study, fasting will be defined as nothing by mouth except water and any essential medications. If a participant is not fasting, the Investigator will reschedule the visit as soon as possible.

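### The SAP's sample logistic code for the exploratory LDL-C targets sets no event level; run as printed, it gives odds ratios for missing the target rather than achieving it

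*SAP*

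**What the plan says.** The endpoint is worded the same way throughout. SAP 2.3.3 lists "Pairwise comparisons among the various treatment groups for the proportion of participants at Day 57 that achieve LDL-C <2.6 mmol/L (<100 mg/dL"), and likewise for the 70 and 50 mg/dL targets. SAP 3.4.3 ("The proportion of subjects at Day 57 that achieve LDL-C <2.6 mmol/L (<100 mg/dL")) and Protocol section 7 ("the proportion of participants at Day 57 that achieve LDL-C <2.6 mmol/L (<100 mg/dL")) also speak of achieving the target.

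For the model, SAP 3.4.3 specifies logistic regression on treatment group and baseline, and gives sample SAS code:

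- The response is described as "LDLC100 = LDL_C value less than 100mg/dL at DAY57 (YES/NO) for example", so YES means the target was reached.
- The procedure call is "proc logistic data= LDL_C", with no other option.
- The only reference level set is for treatment: "Class TREATMENT(ref=0) / Param= Ref", which makes placebo the comparator.
- The model line is "Model LDLC100 = TREATMENT BASE / alpha=0.05 expb plcl plrl orpvalue lackfit".
- The coefficients are exported, and so are the profile-likelihood odds ratios and intervals, through "CLoddsPL= Log_ LDLC100_OddsRatios".

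No text in the SAP says which response level is modelled, or that odds ratios are to be inverted before reporting. SAP section 6 names SAS 9.4 and leaves detailed programming specifications to a separate document.

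**The concern.** The prose asks about reaching the target, while the code leaves the choice of modelled level to the software. A binary response can be modelled in either direction, and the direction decides whether a helpful drug shows an odds ratio above or below 1. The code sets a reference level for treatment but none for the response.

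What is at stake is the direction of the exploratory odds ratios and their intervals. If the default picks failure, the exported data sets for all three targets hold odds ratios for missing the target, although the endpoint is achievement. Because p-values are the same either way, a check on significance alone would not reveal it. SAP 4.2 and 4.3 apply the planned efficacy analyses to an end-of-treatment analysis used in regulatory interactions and to a final analysis used for the clinical study report, so the sample code feeds both.

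**Working it through.** The documents state no odds ratio for these endpoints, so there is no plan figure to reproduce. The check has three steps.

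**1. Which level does the printed code model?**

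The inputs are the YES/NO coding and the code in SAP 3.4.3. The PROC line has no `DESCENDING` or `ORDER=` option, and the response has no `EVENT=` or `REF=` option. I take as an assumption about the software, since the documents do not state it, that PROC LOGISTIC sorts response levels in ascending order and models the first level of a binary response.

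- YES/NO sorts as NO, YES, so NO is modelled.
- Y/N sorts as N, Y, so N is modelled.
- 1/0 sorts as 0, 1, so 0 is modelled.

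Each of these codings models failure to reach the target. The result would differ only if achievement sorted first, for example 1 = yes and 2 = no without a format. The SAP describes no such coding.

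**2. What does that do to the results?**

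Since P(NO) = 1 − P(YES), logit P(NO) = −logit P(YES). Every coefficient changes sign, so:

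- OR(NO) = 1 / OR(YES);
- the confidence limits (L, U) become (1/U, 1/L);
- the test statistics change sign only, and two-sided p-values are the same.

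This is exact for any data with finite estimates, for Wald and profile-likelihood limits alike.

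**3. Numerical illustration.**

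The counts are assumed and say nothing about the effect in this trial. Four arms of 25 were simulated with baseline LDL-C spread evenly over 101 to 174 mg/dL, mean percent changes of 0, −18.58, −30 and −35 for placebo, ezetimibe, obicetrapib and combination, and an SD of 15. Responders below 100 mg/dL were 3, 9, 13 and 15 of 25.

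By hand, without baseline adjustment, combination against placebo:

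- achieving: (15/10) / (3/22) = 1.5 / 0.1364 = 11.0;
- missing: (10/15) / (22/3) = 0.6667 / 7.3333 = 0.0909;
- product: 11.0 × 0.0909 = 1.00.

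With the SAP's model (treatment with placebo as reference, plus baseline) and Wald 95% intervals:

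| Term | OR, event = YES | OR, event = NO | p (both fits) |
|---|---|---|---|
| Ezetimibe vs placebo | 5.926 (1.21 to 29.03) | 0.1687 (0.0344 to 0.8267) | 0.02819 |
| Obicetrapib vs placebo | 12.22 (2.556 to 58.4) | 0.0818 (0.0171 to 0.3912) | 0.00171 |
| Combination vs placebo | 22.44 (4.40 to 114.4) | 0.0446 (0.0087 to 0.2273) | 0.00018 |
| Baseline, per mg/dL | 0.9486 (0.9225 to 0.9754) | 1.054 (1.025 to 1.084) | 0.00021 |

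Before rounding, the product of the two odds ratios is 1.000000 in every row. The right-hand odds ratios are what the printed code returns; the left-hand ones answer the stated endpoint.

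**The case against.** The best case on the other side has five parts.

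- **It is sample code.** SAP 3.4.3 offers it as a sample, with one target as the example, and SAP section 6 defers programming detail to a separate document where the event level would normally be fixed. This stands in part. A reader might infer that the trial's reported odds ratios will be reversed, and the documents do not support that: they show what the printed code does, not what the final programs did. But the code is the only implementation of this model in the documents available, and followed literally it gives the reversed result.
- **The prose is unambiguous.** Both documents say achieve, so a programmer knows the intended event. True, and it is why the code, not the endpoint, needs correcting.
- **No output table is shown.** A reader might infer that a mislabelled table of target achievement will appear. Neither document contains a table shell or a labelling rule, so the finding stops at the exported data sets.
- **The reversal would probably be noticed.** Protocol 9.2.1.2 requires descriptive and graphical summaries by treatment group, and SAP 3.1.4 gives counts and percentages for categorical data. An odds ratio below 1 beside a higher responder percentage is a visible contradiction. This stands, although it is a safeguard after the fact.
- **The endpoints are exploratory.** They lie outside the testing hierarchy, carry nominal p-values only, and can be recovered exactly by inversion. This stands and sets the severity.

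**Conclusion.** The sample code is wrong as written, and the severity is minor. Run as printed on YES/NO or 0/1 data, it models failure to reach the target, so each exported odds ratio is 1/OR of the one intended, the confidence limits are inverted and swapped, and p-values are unchanged. The same holds for the 70 and 50 mg/dL targets if the template is reused.

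This rests on two assumptions: the software's default ordering, and a stored coding in which the failure level sorts first, as it does for the coding the SAP describes. It also requires finite estimates. An arm with no responders, or with only responders, has no finite odds ratio against placebo in either direction, which is a separate matter.

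A reader might go further and conclude that the trial's efficacy findings are affected. They are not: the primary and secondary analyses use the repeated-measures model for percent change, and no sample-size or decision rule depends on these odds ratios.

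**What to change.** In SAP 3.4.3:

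1. Add a sentence stating that the modelled event is achieving the LDL-C target at Day 57, and that an odds ratio above 1 favours achievement in the first-named group.
2. Name the event in the model statement, matching the stored value: `Model LDLC100(event='YES') = TREATMENT BASE / ...` if the variable holds YES/NO, or `event='1'` if it is stored as 1/0. The option must agree with the data, because `event='YES'` does not match a 1/0 variable.
3. Do the same for the variables for the 70 and 50 mg/dL targets, and carry the statement into the separate programming specifications. If those already set the event level, only the SAP text needs aligning.

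The cost is one sentence and one option per model. Data collection, timing and sample size do not change.
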